14.3 Sample Size

For purposes of power calculations, we have applied a Bonferroni adjustment to the alpha level (0.05/2 = 0.025) to allow for two co-primary endpoints. We assume that the effect of both dose and administration mode will be additive (i.e. no interaction). In our sample size calculations shown below we assess the sensitivity of the power to subadditivity of the main effects. Due to the short-term nature of the study, missing data due to loss-to-followup are expected to be rare. In addition, because this study design is testing initial treatment strategies, we do not anticipate problems with adherence to the protocol guidelines.

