2.2 Primary Hypotheses: Route of administration

The primary efficacy hypotheses to be tested in the continuous infusion vs. intermittent bolus comparison are:

- That continuous IV infusion of furosemide causes less renal dysfunction than twice daily IV bolus administration, as measured by change in creatinine from baseline to 72 hours
- That continuous IV infusion of furosemide is more efficacious at relieving acute symptoms compared to twice daily bolus administration, as measured by the area under the curve of serial visual analog assessments for global well being over 72 hours

These hypotheses will be evaluated in the context of a randomized controlled clinical trial using a 2 x 2 factorial design. Each factor (main effect) in the design will be tested at the α =0.025 level.

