11. OUTCOME DETERMINATIONS

11.1 **Primary Endpoints**

This study will use co-primary endpoints

• Change in serum creatinine from randomization to 72 hours

• Area under the Curve (AUC) for Patient Global Assessment by VAS over 72 hours

Rationale for Primary Endpoints:

Change in creatinine from randomization to 72 hours was chosen as the primary safety endpoint due to the observed association between diuretic dosage and worsening renal function and the known association of worsening renal function with other adverse outcomes.

For the assessment of short term efficacy, a variety of endpoints have been utilized in prior AHF studies. These include patient self assessments of symptoms, typically either dyspnea or global well being (termed patient global assessment (PGA)). These self assessments are usually performed using a visual analog scale (VAS) or Likert scale. The DOSE-AHF study will use the PGA by VAS over 72 hours as the primary endpoint for efficacy. The rationale for this choice is that although dyspnea is the primary symptom for most patients with AHF, other symptoms (fatigue, edema, etc) may also be important and should be captured in the primary efficacy endpoint. We have chosen a patient symptom assessment r ather than other measures of diuretic efficacy such as weight change or urine output, because while these measures capture the pharmacodynamic effects of diuretic therapy, they may not be tightly correlated with other clinical events (such as rehospitalization or death), and are therefore not ideal surrogates in the assessment of efficacy.

Patients will be asked to self assess both their general well being and their level of dyspnea using a visual analog scale (VAS) method. For PGA, patients will mark their global well being on a 10 cm vertical line, with the top labeled "best you have ever felt" and the bottom labeled "worst you have ever felt". For dyspnea, the labels will be "I am not breathless at all" and "I am as breathless I have ever been". The VAS is scored from 0 to 100 but the patient is unaware of the numerical value of their response. Patients will self assess both PGA and dyspnea at randomization, 6, 12, 24, 48, 72, and 96 hours. The area under the curve for PGA assessment over the first 72 hours will be the primary efficacy endpoint (AUC for PGA VAS).

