14. STATISTICAL CONSIDERATIONS

14.1 Overview

Means, standard deviations, medians, 25th and 75th percentiles will be presented for continuous variables; the number and frequency of patients in each category will be presented for nominal variables. Statistical tests with a p value < 0.05 will be considered statistically significant, unless otherwise stated. Analyses will be performed using SAS software (SAS Institute, Inc, Cary, NC).

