14.2 Analysis of Primary Endpoints

The primary analysis will be made on an intention-to-treat basis, with patients allocated to the treatment to which randomized. General linear models will be used to examine the effect of each of the main effects on the two co-primary outcomes. The dependent variables in the regression model will be the change in creatinine value from baseline to 72 hours and the AUC for the PGA VAS from baseline through 72 hours. Independent variables in the model will include the main effects of furosemide dose and mode of administration, and the baseline creatinine level. An interaction term will be included if the p-value for that parameter estimate is less than 0.025. For each co-primary outcome, the two main effects will be that the treatment (either dose or mode of administration) has no effect on either of the co-primary outcomes.

We anticipate that some patients may die before all scheduled post-baseline creatinine values can be taken, and that these losses will introduce bias into the main effects comparisons. For the primary analyses, the values imputed will be 0 for the PGA VAS after the time of death and the highest post-baseline creatinine measurement. Sensitivity analyses, including analysis of only complete cases and imputing the worst creatinine value for deaths, will be employed to assess the degree to which these missing values impact the results.

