14.3.1 Change in Creatinine at 72 hours

The standard deviation observed for the change in creatinine from baseline to discharge in the ESCAPE trial (unpublished data) was 0.47 mg/dL. Similarly, in the control arm of the UNLOAD study (unpublished data), the standard deviation of the change in creatinine from baseline to discharge was 0.5 mg/dL. With 300 patients, we will have approximately 88% power to detect a difference in mean creatinine of 0.20 mg/dL for each main comparison, assuming a standard deviation of 0.5 mg/dL. Assuming a smaller standard deviation of 0.4 mg/dL, we would have approximately 98% power to detect a difference of 0.2 mg/dL. The effect of various standard deviations on the power to detect given mean differences in peak creatinine (mg/dL) at the 2.5% significance level is given in Figure 5.

Figure 5. Power with 150 patients per group to detect various mean differences in creatinine (mg/dL) assuming normal distribution with various standard deviations at the two-sided 2.5% significance level

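### Cheap improvement, not an error: within each factor, Holm would keep the 5% familywise bound of the fixed Bonferroni 0.025 and add power when both co-primary endpoints respond

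*Protocol*

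**What the plan says.** Section 11.1 sets the structure: "This study will use co-primary endpoints", namely change in serum creatinine to 72 hours and PGA VAS AUC over 72 hours. Section 14.2 analyses each factor on each endpoint ("General linear models will be used to examine the effect of each of the main effects on the two co-primary outcomes") and words the null as the treatment having an effect on neither: it "has no effect on either of the co-primary outcomes".

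The alpha appears in several places:

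- Section 14.3, for the power calculation: "we have applied a Bonferroni adjustment to the alpha level (0.05/2 = 0.025) to allow for two co-primary endpoints".
- Section 2.2, as a testing rule: "Each factor (main effect) in the design will be tested at the α =0.025 level".
- Section 14.3.1, Figure 5 caption: "various standard deviations at the two-sided 2.5% significance level". The Figure 6 caption uses the same level, and the null row of Table 1 gives the main-effect tests a 2.5% rejection rate.
- Section 14.1, as a default: "Statistical tests with a p value < 0.05 will be considered statistically significant, unless otherwise stated".

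No section describes a step-down or other rule that would release alpha to the second endpoint after the first is rejected. Sections 14.3 and 2.2 attach 0.025 to different things: the first to the pair of endpoints, the second to each factor.

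**The concern.** Sections 2.1 and 2.2 hypothesise a benefit on both endpoints for each factor, and the close of section 4.5 describes the question as a balance of safety and efficacy. A conclusion on both endpoints is therefore part of the planned scenario. With a fixed 0.025, an endpoint with a p-value between 0.025 and 0.05 is declared negative even when the other endpoint has already been rejected at 0.025. A procedure with the same 5% bound for that pair would declare it positive. What is at stake is efficiency on the second endpoint. Validity is not in question, and neither is the stated power.

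**Working it through.** **Inputs.** Creatinine: difference 0.20 mg/dL, SD 0.5 mg/dL (14.3.1). PGA VAS AUC: difference 600, SD 1500 (14.3.2). 150 v 150 patients per factor level, two-sided 0.025 (Figure 5 caption). The correlation between endpoints is not in the protocol, so it is varied. It is signed so that hypothesised benefit is positive on both endpoints. Like the protocol's figures, the calculation ignores covariate adjustment and dropout.

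**1. The plan's own figure.** The standardised difference is 0.20/0.5 = 600/1500 = 0.4 for both endpoints. The noncentrality is 0.4 × √(150/2) = 3.464. Power at two-sided 0.025 is 88.9% (normal approximation) or 88.6% (noncentral t, 298 df), against 88% stated. With creatinine SD 0.4 it is 98.2%, against 98% stated. The protocol's figures reproduce. At two-sided 0.05 the power would be 93.4%.

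**2. Why Holm keeps the bound.** If both nulls are true, any false rejection needs the smaller p-value at or below 0.025, which has probability at most 2 × 0.025 = 0.05. If one null is true, it can be rejected only if its own p-value is at or below 0.05. Neither step uses the correlation. Anything Bonferroni rejects, Holm also rejects.

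**3. Both endpoints at design size, correlation 0.** Write p = 0.8893 (power at 0.025) and q = 0.9337 (power at 0.05).

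- Fixed 0.025, both endpoints: p² = 79.1%.
- Holm, each endpoint: p + (q - p)p = 0.8893 + 0.0444 × 0.8893 = 92.9%.
- Holm, both endpoints: q² - (q - p)² = 0.8718 - 0.0020 = 87.0%.
- At least one endpoint, either rule: 1 - (1 - p)² = 98.8%.

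**4. Other correlations** (4 million simulated bivariate normal pairs; gains taken from unrounded values). Fixed 0.025 gives 88.9% per endpoint throughout.

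| Correlation | Holm, each | Gain, each | Fixed, both | Holm, both | Gain, both |
|---|---|---|---|---|---|
| -0.5 | 93.3% | 4.4 | 78.0% | 86.7% | 8.7 |
| -0.3 | 93.2% | 4.2 | 78.3% | 86.8% | 8.5 |
| 0 | 92.9% | 4.0 | 79.1% | 87.0% | 7.9 |
| 0.3 | 92.5% | 3.6 | 80.4% | 87.5% | 7.1 |
| 0.5 | 92.2% | 3.3 | 81.6% | 88.1% | 6.5 |
| 0.8 | 91.5% | 2.6 | 84.2% | 89.4% | 5.3 |

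**5. Only one endpoint responds, correlation 0.** The responding endpoint gains (q - p) × 0.025 = 0.0444 × 0.025, about 0.1 point. The false-positive rate of the null endpoint rises from 2.5% to 0.025 + 0.025 × 0.889 = 4.7%, still within 5%.

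**6. Across both factors, tests taken as independent.** With all four nulls true, either rule gives 1 - 0.975⁴ = 9.6%. If each factor has one responding and one null endpoint, the chance of any false claim rises from 1 - 0.975² = 4.9% to 1 - 0.953² = 9.2%. Two 5% bounds allow 1 - 0.95² = 9.75% under either rule.

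**The case against.** The strongest case against raising this is that nothing is misstated. Fixed Bonferroni is valid, it reaches the power claimed, and it pairs exactly with 97.5% intervals. Preferring a simple rule in what section 16.1.1 calls a phase II trial is defensible. The Bonferroni sentence in 14.3 is framed as a power assumption, 14.2 states no decision level for the main effects, and an analysis plan that is not shown could set the procedure. This stands as a reason to treat the point as optional. It does not remove the point: section 2.2 says that testing will be at 0.025, and the Figure 5 and 6 captions and Table 1 agree. Testing the second endpoint at 0.05 would therefore depart from the protocol as written.

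It is also fair to say that the gain is conditional. Section 4.3 reports no association between diuretic dose and dyspnoea relief, so an effect on both endpoints is not assured. No section makes success on both endpoints a criterion, so the larger gain measures a target that the trial did not set.

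A reader might infer that Holm within a factor is better whichever family of tests is intended. The documents do not support that. If 2.2 is taken literally, with 0.025 for a whole factor, testing the second endpoint at 0.05 breaks that level. If all four tests form one family, within-factor Holm does not control it, and in the mixed case of step 6 the actual error is nearly doubled. The present rule does not control that family at 5% either.

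**Conclusion.** The point holds as a cheap improvement. Within one factor, Holm dominates the fixed 0.025 at the same 5% familywise bound. Its value is 3.3 to 4.4 points per endpoint and 6.5 to 8.7 points for both, provided that both endpoints have their design-size effects and the correlation lies between -0.5 and 0.5. It is about 0.1 point if only one endpoint responds, and nil for the chance of at least one success.

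A reader might go further and conclude that the trial is underpowered, or that power is lost whatever the truth. Neither follows: 88% is reproduced, and the loss arises only when both endpoints respond. Nor is the actual error rate identical under the two rules. The bound for the pair is the same, but a null endpoint's false-positive rate moves closer to it.

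**What to change.** In 14.2 and 14.3, and in 2.2 to match, state three things:

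- The family is the two co-primary endpoints within each factor, with familywise 0.05 per factor.
- 0.025 is the Bonferroni share of each endpoint.
- The two p-values are tested by Holm: the smaller at 0.025, then the other at 0.05 if the first is rejected.

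The stated 88% then becomes a lower bound. No patient, visit or sample-size change is needed, but the wording must be fixed before unblinding.

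State the costs with it. The 97.5% interval of the second endpoint may include zero although that endpoint is declared positive. The false-positive rate of a null endpoint rises to about 4.7% when the other has its design effect. Error across both factors is not held at 5%, as it is not now.

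If the sponsor instead takes the four factor-by-endpoint tests as one family, apply Holm over all four (0.0125, 0.0167, 0.025, 0.05) and restate the power. In simulation with independent tests, that gives 91.8% per test if all four effects are at design size but 85.4% if only two are, so 88% would no longer be a lower bound.

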14.3.1 Change in Creatinine at 72 hours

The standard deviation observed for the change in creatinine from baseline to discharge in the ESCAPE trial (unpublished data) was 0.47 mg/dL. Similarly, in the control arm of the UNLOAD study (unpublished data), the standard deviation of the change in creatinine from baseline to discharge was 0.5 mg/dL. With 300 patients, we will have approximately 88% power to detect a difference in mean creatinine of 0.20 mg/dL for each main comparison, assuming a standard deviation of 0.5 mg/dL. Assuming a smaller standard deviation of 0.4 mg/dL, we would have approximately 98% power to detect a difference of 0.2 mg/dL. The effect of various standard deviations on the power to detect given mean differences in peak creatinine (mg/dL) at the 2.5% significance level is given in Figure 5.

Figure 5. Power with 150 patients per group to detect various mean differences in creatinine (mg/dL) assuming normal distribution with various standard deviations at the two-sided 2.5% significance level

14.3.2 Change in PGA VAS at 72 hours

For this measure, the maximum possible score on the VAS AUC is 7200 points (100 points x 72 hours). Based on unpublished data from the MEASURE AHF registry, the standard deviation observed for the PGA VAS AUC measure among patients with acute heart failure was approximately 1500 points (over 72 hours). With this standard deviation and the assumed 2.5% significance level, 300 patients will provide 88% power to detect a difference on the PGA VAS AUC of 600 points for each of the treatment factors.

25

Figure 6. Power to detect mean differences in general well-being VAS AUC with 300 patients at the two-sided 2.5% significance level at various standard deviations

In Table 1, we illustrate the sensitivity of the power estimates to hypothetical changes in the mean 96-hour creatinine values across the 4 treatment groups. Scenario 1 corresponds to our assumption of additivity (or no interaction) while scenarios 2 and 3 represent subadditivity and superadditivity, respectively. As expected, the power to detect main effect differences is improved if there is superadditivity of the effects and diminished if there is subadditivity of the effects.

	Low Dose & Infusion	Low Dose & Bolus	High Dose & Infusion	High Dose & Bolus	Power for the main effect tests	Power for the interaction test	Power for the 3 df overall test
Null Scenario	0.1	0.1	0.1	0.1	2.5%	2.5%	2.5%
Scenario 1 – additivity	0.1	0.3	0.3	0.5	88%	2.5%	98%
Scenario 2 – subadditivity	0.1	0.3	0.3	0.3	30%	57%	60%
Scenario 3 – superadditivity	0.1	0.3	0.3	0.7	99%	57%	99%

Table1. Sensitivity of the power to the assumption of additive treatment effects.

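### Table 1 prints 57% power for the interaction test in Scenarios 2 and 3; the stated design gives 30%

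*Protocol*

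**What the plan says.** Section 14.3 sets the significance level: "we have applied a Bonferroni adjustment to the alpha level (0.05/2 = 0.025) to allow for two co-primary endpoints". The caption of Figure 5 in section 14.3.1 makes the tests two-sided: "assuming normal distribution with various standard deviations at the two-sided 2.5% significance level". The base case in that section is "approximately 88% power to detect a difference in mean creatinine of 0.20 mg/dL for each main comparison, assuming a standard deviation of 0.5 mg/dL". Section 5 gives 75 patients in each of the four regimens.

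Table 1 then varies the four cell means; the text above it says that "scenarios 2 and 3 represent subadditivity and superadditivity, respectively". The subadditive row reads "subadditivity 0.1 0.3 0.3 0.3 30% 57% 60", where the last three figures are percentages: power for the main effects, for the interaction (the column headed "Power for the interaction test"), and for the overall 3-df test. The superadditive row (cell means 0.1, 0.3, 0.3, 0.7) also prints 57% for the interaction. The null row, "Null Scenario 0.1 0.1 0.1 0.1 2.5% 2.5% 2.5", shows that all three tests are run at 2.5%.

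Section 14.2 gives the interaction test a role in the primary analysis: "An interaction term will be included if the p-value for that parameter estimate is less than 0.025".

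**The concern.** In a balanced 2x2 design the interaction is a difference of differences over four cells. Its standard error is twice that of a main effect estimated from the same patients. An interaction of 0.2 mg/dL is therefore as hard to detect as a main effect of 0.1 mg/dL, and for a main effect of that size the same table prints 30%. A figure of 57% for the interaction cannot be squared with that.

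The sample size is justified under additivity, and Table 1 is there to show what happens if that assumption fails. In Scenario 2 it fails badly enough to reduce main-effect power to 30%. The printed 57% implies that the interaction test would pick this up more often than not. If the true figure is 30%, the test misses it about 70% of the time. The interaction term would then usually stay out of the co-primary models, and its absence would be weaker support for additivity than the table suggests.

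**Working it through.** **Inputs.** 75 per cell, 300 in total (section 5). Standard deviation 0.5 mg/dL (section 14.3.1, base case; Table 1 does not restate it). Two-sided level 0.025 (sections 14.3 and 14.3.1, null row of Table 1), so the normal critical value is 2.241. Cell means from Table 1, in the order low/infusion (LI), low/bolus (LB), high/infusion (HI), high/bolus (HB). No dropout is applied.

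**Step 1: main effects.** The standard error of a 150 v. 150 comparison is 0.5 × √(2/150) = 0.0577. The dose effect is (HI + HB)/2 − (LI + LB)/2; by symmetry of the cell means the route effect has the same size. Power is from the noncentral F with 1 and 296 df.

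| Scenario | Main effect | Effect/SE | Power | Printed |
|---|---|---|---|---|
| 1 | 0.10 + 0.10 = 0.20 | 3.464 | 88.6% | 88% |
| 2 | 0.30 − 0.20 = 0.10 | 1.732 | 30.3% | 30% |
| 3 | 0.50 − 0.20 = 0.30 | 5.196 | 99.8% | 99% |

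**Step 2: overall 3-df test.** Noncentrality is 75 × Σ(cell mean − grand mean)² / 0.25, with 3 and 296 df.

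| Scenario | Σ of squares | Noncentrality | Power | Printed |
|---|---|---|---|---|
| 1 | 0.08 | 24 | 98.0% | 98% |
| 2 | 0.03 | 9 | 60.1% | 60% |
| 3 | 0.19 | 57 | >99.9% | 99% |

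So a standard deviation of 0.5 and a level of 0.025 reproduce both of these columns.

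**Step 3: interaction.** The contrast is HB − HI − LB + LI.

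- Scenario 2: 0.3 − 0.3 − 0.3 + 0.1 = −0.2.
- Scenario 3: 0.7 − 0.3 − 0.3 + 0.1 = +0.2.
- Standard error: 0.5 × √(4/75) = 0.1155.
- Effect/SE in size: 0.2/0.1155 = 1.732, noncentrality 3.0.
- Power: 30.3% (noncentral F), 30.5% (normal approximation), 30.3% and 30.1% (100,000 simulated trials for Scenarios 2 and 3). Printed: 57%.

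**Step 4: internal consistency, whatever the standard deviation.** Write σ for the standard deviation. In Scenario 2 the main effect is 0.10 with standard error σ√(2/150), and the interaction is 0.20 with standard error σ√(4/75). Since 4/75 is four times 2/150, the second standard error is exactly double the first, and so is the effect. The two ratios are equal for every σ, so the two powers must be equal. The row prints 30% and 57%.

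The 3-df column agrees. Its noncentrality is the sum of the three 1-df components. In Scenario 2 that is 3 + 3 + 3 = 9, which gives the printed 60%. An interaction component of 6, which is what 57% would need, makes the sum 12 and the 3-df power 76%.

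**Step 5: could other settings give 57%?**

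| Setting | Interaction power |
|---|---|
| SD 0.5, two-sided 0.05 | 41% |
| SD 0.5, one-sided 0.025 | 41% |
| SD 0.5, one-sided 0.05 | 53% |
| SD 0.47, two-sided 0.025 | 34% |
| SD 0.4, two-sided 0.025 | 47% |
| SD 0.4, two-sided 0.05 | 58% |

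The last line comes close, but it contradicts the 2.5% entries in the null row, and it would make the Scenario 2 main-effect power 58% and the 3-df power 89%. At the 0.025 level, 57% needs a standard deviation of about 0.36, or about 585 patients, or an interaction of about 0.28 mg/dL.

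**Possible source.** The standard error for comparing two single cells is 0.5 × √(2/75) = 0.0816. Then 0.2/0.0816 = 2.449, and the power is 57.4% (148 df) to 58.2% (normal approximation). This matches the printed figure, but the protocol does not give its method, so it remains an inference.

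**The case against.** The strongest reply is that the figure drives nothing. The 300 patients are justified by main-effect power for creatinine and for the PGA AUC, and that power is right. The rule in section 14.2 operates in the same way whether its power is 57% or 30%. No sentence in the protocol cites 57%, calls the interaction test adequate, or claims that a null result proves additivity. Even 57% is poor power, and Table 1 already discloses correctly that subadditivity reduces main-effect power to 30%. Balanced randomization also keeps the marginal comparisons valid when there is an interaction; what changes is their power and interpretation.

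All of this is fair, and it limits the consequences: no design parameter changes. It does not make the printed number right. The missing standard deviation is no defence, because Step 4 holds for any value. Adjustment for baseline creatinine would change both powers alike. The value appears in two intact rows, so it is not a damaged table. An analysis plan written later would not correct a result printed in the protocol. The column exists to tell the reader how well this trial can detect non-additivity, and it answers that question wrongly in the favourable direction.

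**Conclusion.** The concern holds. Power for the interaction test in Scenarios 2 and 3 is 30%, not 57%, an overstatement by a factor of about 1.9. The 30% rests on 75 per cell, a two-sided 2.5% level and a standard deviation of 0.5 mg/dL. The last of these is inferred for Table 1, but it reproduces every main-effect and 3-df entry outside the null row. The contradiction within the Scenario 2 row needs no assumption about the standard deviation.

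For scale, the interaction test would match the planned main-effect power of 88% only for an interaction of about 0.40 mg/dL (0.40/0.1155 = 3.464, the same ratio as 0.20/0.0577), twice the main effect the trial is designed to detect. This is an error in a stated operating characteristic of a test that selects the primary model, so it should be corrected. It does not affect the sample size or the main-effect power.

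**What to change.** In Table 1, replace 57% by 30% in the Scenario 2 and Scenario 3 rows. State beside the table the standard deviation and significance level used.

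Add one sentence to section 14.3.2: a non-significant interaction test does not establish additivity, because the trial has only about 30% power for an interaction as large as the planned main effect of 0.2 mg/dL.

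The cost is two table cells and a line or two of text. The printed figure becomes less favourable; the sample size, significance levels, endpoints and analysis model stay as they are.
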